[figure not shown]
[figure not shown]

## 2. LIST OF ABBREVIATIONS

Abbreviation	Term
AE	Adverse Event
BSA	Body Surface Area
IEC	Independent Ethics Committee
IRB	Institutional Review Board

PFIZER CONFIDENTIAL

### **4. ABSTRACT**

See [Annex 1](#).

[figure not shown]
PFIZER CONFIDENTIAL

## 5. AMENDMENTS AND UPDATES

Amendment number	Date	Protocol section(s) changed	Summary of amendment(s)	Reason
1	28 May 2021	Section 8.5 Data Management Section 8.6 Data Analysis	Aligning with standard template	Administrative Administrative
2	10 June 2021	Section 4. Abstract Section 5. Milestones	Aligned with Study Report Aligned with Study Report	Administrative Administrative
3	27 July 2021	Throughout Document	Spelling errors	Administrative

PFIZER CONFIDENTIAL

## 6. MILESTONES

Milestone	Planned date	Actual Date
Start of data collection	20 July 2020	20 July 2020
End of data collection	01 August 2020	01 August 2020
Final study report	30 Jun 2021	2020

## 7. RATIONALE AND BACKGROUND

Iraq has over 4 years of experience using Enbrel for treatment of plaque psoriasis (PsO) in patients but the first PsO patients to receive Enbrel was in 2014. The dermatologists at the Baghdad Teaching Hospital observed a positive response from patients on Enbrel and it was discussed during the medical to medical interaction. The difficult to treat sites (scalp, face, skin folds, palms/soles and nails) are a major obstacle in the treatment of PsO. The biological treatment is indicated for moderate-to-severe plaque psoriasis patients with difficult to treat sites. Since there is no local published data and limited regional data regarding the use of Enbrel in Iraqi PsO patients with difficult to treat sites, this study is essential. With the expected number of patients for this study, this would be the largest regional study for the evaluation of data on Enbrel use in Iraqi patients with moderate-to-severe PsO.

## 8. RESEARCH QUESTION AND OBJECTIVES

This study aims to see the efficacy of Enbrel as a biological treatment for PsO in Iraqi patients who have difficult to treat sites at presentation.

**Primary objective:** Efficacy of Enbrel in plaque psoriasis with difficult to treat sites by measuring the following baselines: BSA, PASI and DLQI. A comparison between 6 months after treatment and last visit follow-up will be analyzed.

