## 9. RESEARCH METHODS

### 9.1. Study Design

This is a retrospective analysis of approximately 400 patients that were diagnosed with moderate-to-severe plaque psoriasis with difficult to treat sites. Patients will receive Enbrel as treatment for their disease and will include primary and secondary endpoints.

**Primary objective:** Efficacy of Enbrel in Moderate-to-Severe Plaque Psoriasis with difficult to treat sites by measuring the baselines of BSA, PASI and DLQI and compare it with 6 months after treatment and last visit follow-up during study.

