**Secondary objective:**

- Determine the compliance of patients with Moderate-to-Severe Plaque Psoriasis on Enbrel.
- Will take the baselines of BSA, PASI and DLQI for 6 months after treatment and last visit disease activity index to see the efficacy.
- The patients will be divided into 2 groups according to their adherence to Enbrel. and will be compared between both groups in BSA, PASI and DLQI at 6 months after treatment and last visit disease activity index.

Also the demographic characterization of patients will be obtained (patients age, gender, disease duration, etc.) during data collection.

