#### 9.2.1. Inclusion Criteria

Patients must meet each of the following inclusion criteria to be eligible for inclusion in the study:

1. Moderate-to-severe plaque psoriasis patients who have been receiving etanercept for at least 1-year duration.
2. Have difficult to treat sites at presentation.
3. Age  $\geq 18$  years.
4. No history of using other biological treatments, other than etanercept for the treatment of moderate-to-severe PsO.

PFIZER CONFIDENTIAL

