### **9.6. Data Analysis**

Detailed methodology for summary and statistical analyses of data collected in this study will be documented as below.

All covariates will be summarized to get information about frequency distribution and mean, median or standard deviation. Numbers and percentages will be provided for dichotomous and polychotomous variables when performing descriptive analysis of categorical data. Means, medians, standard deviations and interquartile range as appropriate will be provided for continuous variables when performing descriptive analysis of continuous data.

The bivariate analysis will be conducted to determine if there is any association between the outcome and the exposure (the covariates). Unadjusted comparisons of baseline characteristics for 0, 4, and 12 months after treatment and last visit disease activity index against outcome measures will be provided. Appropriate tests will be used based on the distribution of the measure: chi-square test will be used for categorical variables, t-test will be used for continuous variables, and the Kruskall-Wallis test for non-parametric variables; p-values will also be generated.

No regression model will be built for this analysis.

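### The primary contrast is stated inconsistently: Section 8 leaves out baseline, Section 9.1 includes it, and Section 9.6 has no 6-month time point

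*Combined protocol and SAP*

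**What the plan says.** Section 8 opens with the purpose: "This study aims to see the efficacy of Enbrel as a biological treatment for PsO in Iraqi patients". Its primary objective is efficacy, assessed "by measuring the following baselines: BSA, PASI and DLQI". The next sentence names the comparison: "A comparison between 6 months after treatment and last visit follow-up will be analyzed".

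Section 9.1 gives the same primary objective a different contrast: "measuring the baselines of BSA, PASI and DLQI and compare it with 6 months after treatment and last visit follow-up during study". The secondary objectives in Section 9.1 return to the three indices at 6 months and last visit, once for all patients and once split by adherence.

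Section 9.6, which governs the analysis, announces unadjusted comparisons of "baseline characteristics for 0, 4, and 12 months after treatment and last visit disease activity index against outcome measures". It does not mention month 6 and does not identify a primary comparison.

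On treatment exposure, Section 9.2.1 admits "Moderate-to-severe plaque psoriasis patients who have been receiving etanercept for at least 1-year duration".

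**The concern.** One primary objective has two different contrasts, and the analysis section matches neither in full. The contrast in Section 8 does not contain the baseline reading, yet the plan has no untreated or comparator group, so baseline is the only reference against which improvement could be seen. An analyst who followed Section 8 to the letter would produce a result about what happens after month 6 and would file it under efficacy. An analyst who followed Section 9.1 would produce the change from baseline. One who followed Section 9.6 would have no 6-month result at all.

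What is at stake is whether a reader of the report can tell which result was the planned primary one. Section 9.6 says that p-values will be produced, but no section says which of them answers the primary objective.

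**Working it through.** The plan gives no outcome values, standard deviations, alpha or effect size, so there is no figure to reproduce. The check sets the sections side by side and then uses simple algebra.

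**Time points named**

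| Place | Baseline (month 0) | Month 4 | Month 6 | Month 12 | Last visit | Comparison named |
|---|---|---|---|---|---|---|
| Section 8, primary | measured, not compared | no | yes | no | yes | month 6 vs last visit |
| Section 9.1, primary | yes | no | yes | no | yes | baseline vs month 6; baseline vs last visit |
| Section 9.6 | yes | yes | no | yes | yes | none identified as primary |

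**What each contrast can show**

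Let B, M6 and L be one patient's score at baseline, month 6 and last visit, with higher scores worse.

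- Section 8: M6 − L.
- Section 9.1: B − M6 and B − L.
- For a patient with all three readings, M6 − L = (B − L) − (B − M6). B cancels.

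Three cases follow:

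1. Full response by month 6, held: M6 = L, so M6 − L = 0, while B − M6 and B − L are both large.
2. No response at any time: B = M6 = L, so M6 − L = 0, and B − M6 = B − L = 0.
3. Response by month 6, partly lost later: M6 < L < B, so M6 − L is negative (worsening), while B − L is still positive (improvement).

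Cases 1 and 2 cannot be told apart by the Section 8 contrast. In case 3 the two sections give opposite signs. The Section 8 contrast can be derived from the two Section 9.1 contrasts, but neither of those can be recovered from M6 − L alone.

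**Section 9.6 against the objectives**

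Of the three differences above, only B − L can be formed from the time points listed in Section 9.6. Both B − M6 and M6 − L need month 6, which is not listed. Correcting Section 8 alone would therefore leave the 6-month part of the primary objective without a place in the analysis section.

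**Treatment status at the two later readings**

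If month 6 is counted from the start of Enbrel, it lies inside the 1-year minimum for every eligible patient. The last visit is not dated, and the plan does not say that patients are on drug then. Section 9.1 also states: "The patients will be divided into 2 groups according to their adherence to Enbrel". One group may therefore include interrupted use. The algebra does not depend on this, because B is absent from M6 − L whatever the treatment status at L.

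**The case against.** The strongest reply is that this is a drafting slip. In Section 8 the disputed sentence directly follows one that lists baseline measurements, and there is little reason to list them unless later readings are to be set against them. Section 9.1 spells that comparison out, its secondary objectives bring in baseline again, and Section 9.6 includes month 0. This stands as evidence of intent: the contrast in Section 9.1 is probably what was meant. It does not settle the text. Section 8 is where the research question is stated, its only named comparison omits baseline, and no other section says which version is primary.

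Three stronger readings are tempting and should not be drawn:

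- A reader might infer that the study cannot show improvement at all, or that a stable response would be reported as lack of efficacy. The documents do not support this. Baseline is recorded, Section 9.1 uses it, and there is no hypothesis or success criterion under which a zero difference after month 6 would count as failure.
- A reader might infer that both Section 8 readings are on treatment, so that the contrast is purely one of maintained response. That is certain only for month 6; for the last visit it is an inference from the entry criterion.
- A reader might infer that using the Section 9.1 contrast would establish efficacy. It would not. It is a before-after change without a control group, in patients selected for having stayed on etanercept for at least 1 year.

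**Conclusion.** The point holds as an inconsistency in the primary contrast across Sections 8, 9.1 and 9.6. Taken literally, Section 8 describes change after month 6 and carries no information about improvement from baseline. Section 9.1 does carry that information and is the likely intent. Section 9.6 cannot deliver the 6-month part of either version.

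No numerical size can be given, because the documents contain no outcome data or assumptions, and the conclusion needs none. It rests on the wording of the three sections, on the cancellation of B in M6 − L, and on month 6 being counted from the start of Enbrel. It does not rest on treatment status at the last visit.

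The defect should be corrected because it concerns the primary objective and costs little to remove. It does not show that the wrong analysis was or will be done.

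**What to change.** 1. In Section 8, replace the comparison sentence with: within-patient change in BSA, PASI and DLQI from pre-Enbrel baseline to 6 months, and from pre-Enbrel baseline to last visit. Use the same words in Section 9.1.
2. If 6 months versus last visit is of interest, list it as a separate secondary comparison, labelled maintenance of response. Say how the last visit is defined and whether patients are on Enbrel at that visit.
3. In the same edit, reconcile the time points in Section 9.6 with the objectives: add month 6, state which comparisons are primary, and either give months 4 and 12 a stated role or remove them.
4. In the limitations and in the report, describe the result as an uncontrolled before-after change in patients selected for at least 1 year of treatment.

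The cost is one sentence in Section 8, matching edits in Sections 9.1 and 9.6, and a line in the limitations. No readings are needed beyond those Section 9.1 already assumes. The documents do not confirm that the registry extract holds month-6 values rather than values at months 4 and 12, so check this before the wording is settled. The milestones show data collection as complete, so the edit should be dated and the report should say that the contrast was clarified afterwards.

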**Secondary objective:**

Determine the adherence of patients to the biological treatment.

## 9. RESEARCH METHODS

### 9.1. Study Design

This is a retrospective analysis of approximately 400 patients that were diagnosed with moderate-to-severe plaque psoriasis with difficult to treat sites. Patients will receive Enbrel as treatment for their disease and will include primary and secondary endpoints.

**Primary objective:** Efficacy of Enbrel in Moderate-to-Severe Plaque Psoriasis with difficult to treat sites by measuring the baselines of BSA, PASI and DLQI and compare it with 6 months after treatment and last visit follow-up during study.

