### **9.2.2. Exclusion Criteria**

Patients meeting any of the following criteria will not be included in the study:

1. Etanercept use for treatment of moderate-to-severe PsO less than 1-year duration.
2. Previous use of another biological treatment for treatment of moderate-to-severe PsO.

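### The last-visit time point in the primary objective and in the adherence comparison has no fixed treatment duration, and the analysis neither reports duration nor stratifies by it

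*Combined protocol and SAP*

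**What the plan says.** Section 9.1 measures BSA, PASI and DLQI at baseline and will "compare it with 6 months after treatment and last visit follow-up during study". Section 8 words the primary contrast differently: "A comparison between 6 months after treatment and last visit follow-up will be analyzed". Neither section gives the last visit a target month, a window, a maximum or a cut-off rule. The secondary objective in Section 9.1 uses last visit again, with month 6, to compare two groups defined by adherence.

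Inclusion criterion 1 (Section 9.2.1) admits "Moderate-to-severe plaque psoriasis patients who have been receiving etanercept for at least 1-year duration". Section 9.2.2 excludes "Etanercept use for treatment of moderate-to-severe PsO less than 1-year duration". These set a floor of 1 year and no ceiling. On calendar time, Section 7 says that "the first PsO patients to receive Enbrel was in 2014" and also that "Iraq has over 4 years of experience using Enbrel for treatment of plaque psoriasis". Section 6 puts data collection between 20 July and 1 August 2020.

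Section 9.6 lists "0, 4, and 12 months after treatment and last visit disease activity index", so it has month 12 but not month 6. It plans unadjusted comparisons by chi-square, t and Kruskal-Wallis tests and rules out a regression model. Treatment duration at last visit is not summarised, stratified by or adjusted for. Section 9.8 names missing data as the only limitation.

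**The concern.** A score at month 6 answers a defined question. A score at last visit, pooled over patients who may have had 1 year or several years of treatment, does not: its mean depends on when the registry's patients started as well as on how they respond. The reader of the report could not attach the last-visit result to any time on treatment.

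The adherence comparison is more exposed. If the two groups differ in time since start at their last visit, and scores change with time on treatment, part of the difference between groups comes from follow-up length. Nothing in the planned output would show whether this had happened, and a larger sample would not remove it.

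**Working it through.** The plan states no follow-up duration, so there is no figure to reproduce. The possible span follows from its dates.

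**Inputs**
- Minimum duration: 1 year (Sections 9.2.1 and 9.2.2).
- Earliest start: 2014, month not given (Section 7), so 1 January to 31 December 2014 is used.
- Latest possible last visit: 20 July to 1 August 2020 (Section 6).
- Alternative maximum: just over 4 years, if the statement about years of experience in Section 7 governs.

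**Longest possible duration at last visit** = (data-collection date - first start) / 365.25 days

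| First start | to 20 July 2020 | to 1 August 2020 |
|---|---|---|
| 1 January 2014 | 6.55 years | 6.58 years |
| 1 July 2014 | 6.05 years | 6.09 years |
| 31 December 2014 | 5.55 years | 5.59 years |

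The possible span is therefore 1 year to about 5.6-6.6 years. On the alternative reading it is 1 year to just over 4 years. The longest possible duration is at least 4 times the shortest on either reading.

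**Interval in the Section 8 contrast (month 6 to last visit)**
- Shortest: 1 - 0.5 = 0.5 year.
- Longest: 5.6 - 0.5 = 5.1 to 6.6 - 0.5 = 6.1 years (just over 3.5 years on the alternative reading).

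**What the pooled result estimates.** Let m(t) be the mean score at t years on treatment and p(t) the share of patients whose last visit is at t. The pooled last-visit mean is the sum of p(t) x m(t). Unless m(t) is flat after year 1, it changes with p(t), which the plan neither fixes nor reports.

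**What the adherence comparison estimates.** Suppose scores change by b points a year, and the groups' mean times to last visit differ by d years. The unadjusted difference is then the adherence difference plus b x d. The documents give neither b nor d. With purely assumed values of b = 0.25 to 1.0 point a year and d = 0.5 to 2 years, b x d runs from 0.25 x 0.5 = 0.125 to 1.0 x 2 = 2.0 points. This sixteen-fold range shows that no size can be stated from the documents.

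**The case against.** The strongest reply is that the primary objective already has a fixed time, month 6, which this point does not touch, and that last visit is an understandable descriptive outcome in a retrospective registry study. Both statements are fair. Last visit need not be dropped, and reporting time since start beside it would meet much of the concern. What remains is that last visit is part of the primary objective and of a between-group comparison, with no duration reported for either.

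Three stronger readings are tempting, and the documents support none of them.

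- **Every patient is read at a different duration, over a range of 1 to 6 years.** The text supports only that the duration is not fixed. The span is what the dates allow. Its floor assumes that the last recorded visit falls after the qualifying year, which is not stated.
- **Late last visits belong only to patients who stay on treatment because they respond.** No rule says that registry visits stop when treatment stops. Criterion 1 can be read as covering patients still on the drug. Time to last visit would then be set largely by start date.
- **The distortion exceeds the sampling error.** A gap between the shortest- and longest-followed patients cannot be set against the 95% half-width of a mean of 400, because these are different quantities. For two groups of 200 with an SD of 6 to 10 (all assumed), the half-width of the difference is 1.96 x SD x sqrt(2/200) = 1.2 to 2.0 points. Most of the assumed range for b x d lies below that.

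A further objection concerns the remedy. Regression adjustment for duration would conflict with Section 9.6. It could also introduce bias if duration is itself a consequence of response or adherence. This stands, and the fix below does not rely on such adjustment.

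**Conclusion.** The concern holds in a limited form. As written, the last-visit result refers to no stated time on treatment. Unequal follow-up between the adherence groups, if present, could not be told apart from an adherence effect. The possible span is about 1 year to 5.6-6.6 years, or to just over 4 years on the other statement in Section 7. It rests on the 1-year floor, first use in 2014, data collection ending on 1 August 2020, and the last recorded visit falling after the qualifying year.

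The existence of the problem follows from the text. Its direction and size do not: they depend on the change in scores over time and on the distribution of follow-up, and the documents give neither. A reader might infer that the last-visit result, or any adherence difference, is known to be biased. The documents show only that the planned analysis could not detect or separate such a bias. The month-6 comparison is unaffected, apart from month 6 being absent from the list in Section 9.6.

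**What to change.** 1. **Time points.** Reconcile Sections 8, 9.1 and 9.6, which now set month 6 in the objectives against months 0, 4 and 12 in the analysis and describe the primary contrast in two ways. Add month 12, with a visit window, as the fixed long-term time point beside month 6. Section 9.6 already lists month 12, and the inclusion rule means that eligible patients have had at least that much treatment.
2. **Last visit.** Report it descriptively, with the distribution of time since first dose and with results by duration band set in advance, for example 1 to <2, 2 to <4, and 4 or more years.
3. **Adherence groups.** Compare them at the fixed time points, and at last visit only within duration bands. This needs no regression model and so agrees with Section 9.6. State that duration may itself be affected by response or adherence, so that the fixed-time comparison is the one to rely on.

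The cost is protocol wording, one derived variable (months since first dose, if the registry holds the dates) and some extra tables. No new patients are needed. There are two downsides. Having been treated for 12 months does not guarantee a visit then, so patients with no recorded visit in the window drop out of that time point and their number should be reported. Each band is also smaller than the full sample, so its estimates are less precise.

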**Secondary objective:**

- Determine the compliance of patients with Moderate-to-Severe Plaque Psoriasis on Enbrel.
- Will take the baselines of BSA, PASI and DLQI for 6 months after treatment and last visit disease activity index to see the efficacy.
- The patients will be divided into 2 groups according to their adherence to Enbrel. and will be compared between both groups in BSA, PASI and DLQI at 6 months after treatment and last visit disease activity index.

Also the demographic characterization of patients will be obtained (patients age, gender, disease duration, etc.) during data collection.

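### The adherence groups have no time window and the same groups serve the 6-month comparison, so adherence after month 6 can decide which group a 6-month score falls in

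*Combined protocol and SAP*

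**What the plan says.** The secondary objective in section 9.1 has one sentence on grouping, "The patients will be divided into 2 groups according to their adherence to Enbrel", and continues that they will be "compared between both groups in BSA, PASI and DLQI at 6 months after treatment and last visit disease activity index". One division is described, and it serves both time points.

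Adherence otherwise appears only as an aim: "Determine the adherence of patients to the biological treatment" in section 8 and "Determine the compliance of patients with Moderate-to-Severe Plaque Psoriasis on Enbrel" in section 9.1. Neither place gives a definition, a cut-off, a data item or a measurement period.

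Eligibility in section 9.2.1 requires "Moderate-to-severe plaque psoriasis patients who have been receiving etanercept for at least 1-year duration"; sections 9.2 and 9.2.2 agree. Section 7 says that "the first PsO patients to receive Enbrel was in 2014", and section 6 dates data collection from 20 July to 1 August 2020. The design is retrospective, on about 400 patients.

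Section 9.6 plans unadjusted bivariate tests without regression. It lists months 0, 4 and 12 and the last visit, but no 6-month point. Section 9.8 names missing data as the only limitation.

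**The concern.** In a retrospective extraction, whatever adherence history exists is already complete when the groups are formed. With no window set, a patient who took treatment fully to month 6, responded poorly and then missed doses can be classed as non-adherent. That patient's poor 6-month score then counts against non-adherence that had not yet occurred.

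If good early response makes patients more likely to continue as prescribed, the adherent group will look better at 6 months even if adherence does nothing. This differs from baseline confounding. Adjusting for age, gender or baseline severity would not repair it, because part of the exposure is measured after the outcome. A reader of the results could not tell which analysis had been done, or whether the 6-month difference says anything about adherence.

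**Working it through.** The plan gives no figure to reproduce. The study size is stated without alpha, power, effect size or SD, and no adherence rate is given. The check has three parts.

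**1. Share of the treatment period after the 6-month score.** Taking month 6 as counted from the start of etanercept, a patient with T months on treatment has a share (T − 6)/T after the score.
- T = 12 (the minimum in section 9.2.1): 6/12 = 50%.
- T = 24: 18/24 = 75%.
- T = 72 (roughly 2014 to 2020, sections 6 and 7): 66/72 = 92%.

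So at least half of every patient's treatment period follows the score. This is time on treatment; the documents do not say how long an adherence record the registry holds.

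**2. Size of a spurious gap when adherence has no effect.** All inputs are assumed. Let half of patients respond at 6 months, and let a and b be the proportions of responders and non-responders later classed as adherent. Then:
- response among adherent = 0.5a / (0.5a + 0.5b)
- response among non-adherent = 0.5(1 − a) / [0.5(1 − a) + 0.5(1 − b)]

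Results:
- No link (a = b): both are 50%, a gap of 0 points.
- Weak link (a = 0.75, b = 0.65): 0.375/0.700 = 53.6% and 0.125/0.300 = 41.7%, a gap of 12 points.
- Stronger link (a = 0.85, b = 0.60): 0.425/0.725 = 58.6% and 0.075/0.275 = 27.3%, a gap of 31 points.

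**3. The same question on a continuous score.** This was a null simulation with assumed inputs: 400 patients, 4,000 runs per scenario and a two-sided t-test at 0.05. Adherence in months 0 to 6 was unrelated to the 6-month score. Later adherence fell as the score worsened, with correlation ρ in absolute size. The non-adherent share was 30% or 50%. With groups formed on the whole record:

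| Record length | ρ = 0.1 | ρ = 0.2 | ρ = 0.3 |
|---|---|---|---|
| 12 months: difference; false positives | 0.12 SD; 19–20% | 0.23 SD; 59–63% | 0.34 SD; 89–93% |
| 24 months: difference; false positives | 0.15 SD; 29–34% | 0.31 SD; 83–86% | 0.46 SD; 99% or more |

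With ρ = 0 the false-positive rate was 4.5–5.3%. With groups formed on months 0 to 6 only, it was 4.4–5.8% in every scenario. That last result follows from the assumption that adherence before month 6 is unrelated to the score. It shows that the window removes this particular route of bias, not every route.

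**The case against.** The strongest reply is that the problem is read out of silence. The plan never says that adherence after month 6 will be counted. The grouping sentence is broken in the text and does not rule out forming groups separately at each visit. On this view the real gap is that adherence is undefined, and the missing window is one part of it. This stands as far as wording goes: a reader might infer that later adherence *is* used, but the documents support only that it *can* be. The point survives because one division applied to both visits is the natural reading, and a definition with a cut-off but no window would leave the time order unresolved.

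A reader might also infer that most of the adherence record falls after month 6. At the 1-year minimum it is exactly half of the treatment period, and the length of the adherence record is not given.

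A third tempting reading is that the study will claim an adherence benefit. The plan says only that groups will be compared and that association will be tested, within a secondary objective. The risk lies in how the contrast is interpreted.

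The sizes are also fairly challenged. They rest on assumed inputs and vanish if later adherence is unrelated to 6-month response. The responder outcome in the arithmetic is not one the plan defines. Excluding patients with under 1 year of etanercept removes early stoppers, so the assumed proportions need not describe this cohort.

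Finally, the remedy is partial. Adherence before month 6 can itself respond to early improvement or failure. At last visit, adherence up to that visit is close to the whole record, and earlier disease activity can drive it. This stands and belongs among the stated limitations.

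**Conclusion.** The concern holds in this form: with no adherence window and one pair of groups used at both visits, adherence after month 6 can determine the groups for the 6-month scores, and sections 9.6 and 9.8 neither prevent nor acknowledge it. The 6-month contrast is therefore open to reverse causation.

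How large the bias is cannot be known from the documents. The illustrations run from 0 to 31 points, depending wholly on an assumed link between early response and later adherence that the plan neither excludes nor addresses. The matter affects a secondary comparison and should be corrected. It does not bear on the primary before-and-after comparison.

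**What to change.** In sections 9.1 and 9.6:
- For the 6-month contrast, classify adherence only from first dose to month 6.
- For the last-visit contrast, use adherence up to that visit and not beyond.
- State one adherence definition and one cut-off, applied at both time points.
- Reconcile the 6-month point in section 9.1 with the months 0, 4 and 12 listed in section 9.6, since the window cannot be anchored until they agree.

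In section 9.8, state that earlier disease activity can drive adherence before either score, so these windows reduce reverse causation but do not remove it, least of all at last visit.

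If the registry holds no dated adherence data, the 6-month classification cannot be made. In that case label the 6-month contrast descriptive, do not interpret it as an adherence effect, and add the time-order limitation to section 9.8.

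The cost is a few sentences and, if dated data exist, a second derived grouping; no section confirms that they do. Fewer patients are likely to be classed as non-adherent by month 6, so that contrast loses precision. Data collection ended on 1 August 2020, so the change may have to be a documented reanalysis that says when the cut-off was chosen.
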